3.11 Data

3.11.1 Datasets and coding

Some study sites may not be able to collect all information proposed above. Study sites can indicate which variables they can collect and which data source they will use in Annex 1: 'List of variables collected, definition and coding'. Study sites can use the coding (variable names and values) as specified in Annex 1 or use their own coding. For the pooled analysis, if study site-specific coding is used, a data dictionary can be supplied alongside the data.

3.11.2 Data collection instruments

Data will be collected using a standardised questionnaire/data collection form. Some information may require follow-up. The source(s) of data may include:

- face-to-face/telephone interview;
- electronic medical records;
- interview with patient or their family;
- vaccination and other registries;
- laboratory records.

➤ *Each study site to define the sources of information used for each variable collected (see also Annex 1).*

3.11.3 Data collection validation

If paper questionnaires are being used, a sample of paper questionnaires will be checked against the study database to validate data entry.

For GPs using electronic medical records, a sample of patients can be asked to fill a questionnaire and questionnaire results can be compared to the medical records and the study database.

➤ *The specific validation procedures, including sample size calculation for questionnaire validation (if applicable) should be specified in the study annexes. Vaccination status, date, dose(s) if relevant and vaccine brand should be collected carefully and validated.*

3.12 Data management

3.12.1 Data collection, entry, and storage at study site level

Web-based data collection methods or paper-based methods can be used. Data entry procedures will include checks to minimise data entry errors.

Laboratory information will be reported to the surveillance site coordinator using the reporting procedures existing in each study site for influenza and COVID-19 surveillance.

Information on antigenic, when available, and genetic analyses, including GISAID accession number can be included in the epidemiological database or stored separately on an Excel spreadsheet (see Annex 2).

All data should be stored and processed in a way compliant with GDPR.

- *Study sites to specify procedures of data collection and data entry.*
- *Study sites to specify methods of data storage and their compliance with the GDPR requirements.*
- *Study sites to provide a data dictionary (codebook) that includes the variable names, variable descriptions, and the coding of variable values (see also Annex 1).*

3.13 Analysis

3.13.1 Individual (country/study site level) analysis

The timing to conduct such analyses will depend on the epidemiological situation and the sample size achieved. Example scripts can be provided if desired, and support is available for analysis.

Cases and controls will be described by baseline characteristics. Patients will be described according to:

- sex;
- age group;
- time: month of symptom onset;
- influenza (IVE) or COVID-19 vaccination status (CVE);
- absence, presence of at least one, or presence of more than one high-risk condition;
- specific chronic conditions (e.g. diabetes, immunodeficiencies, respiratory diseases, cardiovascular diseases);
- pregnancy;
- vaccination status of other vaccines;
- respiratory co-infections.

An example layout of this descriptive analysis is provided in Table 5 below.

Table 5. Example of descriptive table for cases and controls; COVID-19/influenza vaccine effectiveness study at primary care level, country X, year

Variables	Number of laboratory-confirmed COVID-19 (or influenza) cases/total n (%)	Number of test-negative controls/total n (%)
Median age (IQR)	X	X
Missing	X	X
Age groups (years)		
0–14	x/x (x)	x/x (x)
15–45	x/x (x)	x/x (x)
45–64	x/x (x)	x/x (x)
65–79	x/x (x)	x/x (x)
≥80	x/x (x)	x/x (x)
Missing	X	X
Sex		
Female	x/x (x)	x/x (x)
Missing	X	X
Days between onset of symptoms and swabbing		
0	x/x (x)	x/x (x)
1	x/x (x)	x/x (x)
2	x/x (x)	x/x (x)
3	x/x (x)	x/x (x)
4–7	x/x (x)	x/x (x)
8–10 (if CVE)	x/x (x)	x/x (x)
COVID-19/influenza vaccination status	x/x (x)	x/x (x)
Missing	x	X
Etc.		

In a second step, a univariable analysis will be carried out to measure the association between vaccination and being a laboratory-confirmed influenza or COVID-19 case. This study is a case-control study (test-negative design). The measure of association is an odds ratio (OR). This can be estimated by logistic regression. An OR = 1 indicates no association between an exposure and the outcome. An OR > 1 indicates a potential risk factor, an OR < 1 indicates a potential protective factor, noting that the confidence interval around the OR helps with its interpretation.

For vaccination as preventive factor, the IVE/CVE can be computed as $IVE/CVE = (1 - OR) * 100$. The logistic regression model computes a 95% confidence interval around the point estimate of the OR, and the same formula as above can be used to obtain the VE 95% confidence interval.

A crude VE for the IVE/CVE against being a laboratory-confirmed influenza/COVID-19 case will be estimated.

A stratified analysis (by sex and age group, for example) can follow to better understand potential effect modifiers and confounders.

Prior to multivariable analysis, a model development strategy should be determined (see also Annex 4). Creating direct acyclic graphs may help better understand how the variables relate to each other and the outcome. In a final step, a multivariable analysis will be carried out to take confounding factors and potential effect modifiers into account. Please see Annex 4.

Output tables presenting IVE/CVE estimates

To present the results in the most transparent manner and to enable the reader to best understand the data, tables similar to the one illustrated by Table 6 below can be used (variables presented just as example of the output format). Useful information includes numbers of cases and controls (overall and vaccinated) and presentation of results for different models.

Table 6. Example of table displaying vaccine effectiveness against COVID-19/influenza adjusted for various covariables overall and by age group; COVID-19/influenza vaccine effectiveness study at primary care level, country X, year

Clade/variant	Population included	Analysis scenarios/adjustments made	CVE (or IVE) (%)	(95%CI)
COVID-19 (or influenza)	All ages	N (cases/vaccinated; controls/vaccinated)		
		Crude		
		Adjusted for onset date (cubic spline)		
		Adjusted for sex		
		Adjusted for chronic condition		
		Adjusted for age (cubic spline)		
		Adjusted for onset date, age (cubic spline)		
		Adjusted for onset date, chronic condition		
		Adjusted for onset date, age (cubic spline), chronic conditions, sex		
		0–49 years	N (cases/vaccinated; controls/vaccinated)	Crude
Adjusted for onset month, age (cubic spline)				
50 years and over	N (cases/vaccinated; controls/vaccinated)			Crude
		Adjusted for onset date, age (cubic spline), chronic condition, sex		

3.13.2 Sensitivity analyses

As sensitivity analyses, study sites can measure VE:

- with different cut-offs of numbers of days between onset and swabbing;
- with different cut-offs of numbers of days between vaccination and onset of symptoms;
- varying the time period post-vaccination (e.g. seven days, 14 days, 15-30 days, 30-59 days, etc.) to be considered 'fully vaccinated' or 'partially vaccinated' (see section 3.8.1);
- including, excluding and stratifying by those with previous positive tests, and also with different delays between previous test and inclusion in the study;

- excluding patients testing positive at home as part of the current illness episode and testing negative as part of the study;
- using only controls positive to other respiratory viruses;
- excluding controls testing SARS-CoV-2 positive (IVE) or influenza positive (CVE), or adjusting by COVID-19 (IVE) or influenza (CVE) vaccination (see also section 5.1.7);
- including those fully vaccinated but with inappropriate gaps between doses.

3.13.3 Pooled analysis

The higher sample size for the pooled analysis will provide more precision around the VE estimates. Data can be coded as outlined in Annex 1, or a data dictionary can be provided by the study teams that includes the variable names, descriptions and coding. The central hub (performing the pooled analysis) will perform data cleaning and document and share any further data cleaning and analysis with all study coordinators to ensure it can be reproduced.

See Annex 4 for detailed guidelines for analysis, including the pooled analysis. For the pooled data, interim analyses will be conducted in different periods if appropriate and according to the available sample size.

The timing to conduct each interim analysis will depend on the time needed to reach the appropriate sample size. This will depend mainly on the incidence of influenza (for IVE) or COVID-19 (for CVE), vaccination coverage, the recruitment strategy and the number of participating primary care practices.

The pooled analysis will be carried out in a similar way to the study site-specific analysis. Country or study site will be included as a fixed effect or potentially as a random effect in a multilevel model. Statistical heterogeneity between study sites will be determined, using the Q-test and the I^2 index.

3.14 Personal data protection

Each study site conducting the study shall comply with requirements stemming from data protection legislation, and with national ethics committee requirements. Where required, informed consent will be sought from all participants or legal guardians. The national ethics committees will specify whether oral, written, or no consent will be required. A copy of the ethical approvals should be sent to the coordinating centre.

Ethical approval and consent forms should state that the patient's data will be used for a multicentre study and results will be shared with the scientific community (articles, presentations, etc.).

- *Each study site to describe the procedures to comply with the national ethics committee requirements and the type of informed consent needed as well as whether consent can be obtained from a legal guardian.*
- *Each study site to send a copy of the ethical approval to the coordinating centre.*

3.15 Safety

During consultations, during the swabbing procedure and during handling of biological specimens, the safety of the practitioners is paramount. Any person swabbing, handling swabs and swabbing material, should be fully trained and ensure that adequate personal protective equipment is used and hygiene measures followed, according to national and clinic-specific guidelines.

- *Each study site to state the safety measures carried out, related to swabbing, handling of biological specimens, transport of samples, authorisation levels of biologists, biosafety levels of laboratories, etc.*

3.16 Training

Investigators and data collectors will be trained on the study protocol before the start of the study. They will receive the protocol and questionnaires.

The target audience and material for training will depend on the data collection methods (e.g. GP interviews, electronic database usage) and the dataflow structures in place. This could include training videos, paper-based training material and practice visits. Special emphasis should be put on the systematic selection of patients to swab, in terms of importance and logistics.

- *Each study site to describe the training to be organised.*

4 Logistical aspects

4.1 Study site leader

In each study site, a study site leader will coordinate the study at the country level and act as focal point for a pooled analysis.

4.2 Human resources

In each study site, an investigator will be in charge of monitoring data collection at the GP office level. GPs will collect the information among consulting patients. The specific human resources needed in each country are detailed in the study annexes.

5 Limitations

Any observational study is subject to an array of biases, some of which are outlined below. Other limitations include, in the context of a new SARS-CoV-2 variant causing more severe disease or a very severe influenza season, that primary care systems may become disrupted or overloaded, making data collection difficult.

5.1 Potential biases

5.1.1 Bias from pooled estimates

With data from study sites from different countries being pooled, any bias in the individual studies will influence the pooled estimate. The power of the test for the presence of heterogeneity between individual studies is low if there are few sites/countries. In this case, the test may not be able to detect heterogeneity between them, despite it being present. It is important that heterogeneity is also assessed using qualitative knowledge about differences between studies. Depending on the nature of the bias, the inclusion of biased studies in the pooled estimate could lead to over- or underestimation of the true association between influenza/COVID-19 vaccination and the outcome.

There are many conditions which could lead to bias in a study site. For CVE, being a novel virus, there are evolving surveillance systems and strategies in each participating country. There are different tests being used (PCR and rapid antigen tests), potentially for different age groups and with changes over time, which may impact how the SARS-CoV-2 outcome is defined (particularly if rapid antigen tests are used for defining the SARS-CoV-2 outcome). Additionally, home testing may affect who sees a GP for an ARI or ILI episode, as knowing their SARS-CoV-2 status may affect whether people consult their GP (which may be differential by vaccination status).

To allow for complete assessment of heterogeneity, study sites need to document all changes in their influenza and COVID-19 surveillance system/s during the study period.

- *Each country to document any changes in influenza/COVID-19 surveillance during the study period.*

5.1.2 Negative confounding

Negative confounding refers to biases that reflect the fact that high-risk groups (people more likely to develop symptomatic infection) will be more likely to be vaccinated and therefore reduce CVE/IVE. If negative confounding is present, the IVE/CVE will be underestimated. Adjustment for potential negative confounding factors documented in the study (e.g. presence of chronic diseases) will minimise negative confounding.

5.1.3 Positive confounding

Positive confounding refers to biases that reflect a 'healthy vaccinee effect'. People with a healthy lifestyle will be more likely to accept vaccination, and may be less likely to become infected, thus leading to an increase of measured CVE/IVE. People with risk-taking behaviours may also be averse to vaccination, which may also increase their exposure to disease. If positive confounding is present, IVE/CVE will be overestimated.

5.1.4 Unmeasured confounding

Positive and negative confounding will be minimised through stratification and multivariable analysis. The test-negative design used here may help overcome some of the unmeasured/difficult to measure confounding. Unmeasured confounding could include heterogeneity of exposures among unvaccinated and vaccinated (the distribution of high-risk behaviours may differ between these groups). It will not be possible to rule out the presence of characteristics in the study population for which no information is collected in the study questionnaire and that therefore could lead to positive or negative confounding. Therefore, as in any observational study, some residual unmeasured confounding may remain.

- *Each study site to describe the potential limitations and representativeness of the subjects included.*

5.1.5 Previous infection in cases or controls

People who have been previously infected may have a stronger response to the vaccine or be less likely to be reinfected even if unvaccinated. It is possible that some of the controls (those testing negative for influenza/SARS-CoV-2) may have themselves been positive for influenza/SARS-CoV-2 some time before. The proportion of these (potentially immune individuals) in each country's dataset would depend on the circulation of the virus in the community in the months before the patient presented to the GP. Knowledge of their prior infection could affect their likelihood to be vaccinated. For example, if someone knew that they had had COVID-19, despite having no symptoms (e.g. if they had had a screening test), they may be subsequently less likely to be vaccinated. This would lower vaccination coverage among controls and decrease CVE. Similarly, if someone believed that they had

had influenza but had not had a test, they may be subsequently less likely to be vaccinated. This would lower vaccination coverage among controls and increase IVE.

Ascertainment of which controls may have had previous influenza/SARS-CoV-2 infection can be attempted by asking about previous influenza/SARS-CoV-2 tests and results, as well as prior clinical symptoms. However, there could potentially be several patients with prior SARS-CoV-2 or influenza infection, unbeknownst to them. Results should be interpreted in light of this, and an estimate of a range of potential bias should be calculated around the IVE and CVE estimates. Sensitivity analyses should be conducted including any patients with previous influenza (IVE) or SARS-CoV-2 (CVE) infection confirmed either by PCR or by serological tests.

5.1.6 Validation of exposure

The vaccination status is the exposure of interest, and therefore reliable vaccination data are critical. If the vaccination status is only self-reported, without written or electronic documentation, information bias may occur. Vaccination status of cases and controls should ideally be validated using an independent source (i.e., vaccination register, GPs database, patient's medical record).

5.1.7 Inclusion of influenza-positive controls for CVE and SARS-CoV-2-positive controls for IVE

A key prerequisite of the test-negative design is that the vaccination of interest does not affect the control group. However, there may be a strong correlation between those receiving influenza and COVID-19 vaccine. If this is the case, inclusion of SARS-CoV-2-positive controls may artificially lower the vaccine coverage among influenza test-negative controls, biasing towards a lower IVE. Conversely, inclusion of influenza-positive controls may artificially lower the vaccine coverage among SARS-CoV-2 test-negative controls, biasing towards a lower CVE. The test-negative design is no longer valid.

To account for this, analyses should be carried out excluding SARS-CoV-2-positive controls (IVE) and influenza-positive controls (CVE), if adequate information is available [27]. These estimates can be compared to the primary analysis of including SARS-CoV-2-positive/influenza-positive controls. An alternative method to account for this potential bias is to adjust by COVID-19 vaccination (IVE) or influenza vaccination (CVE) if this information is available [27].

Sensitivity analyses will be conducted excluding controls who are positive for SARS-CoV-2 from IVE estimation, and excluding controls who are positive for influenza from CVE estimation.

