3.5.4 Other control groups (optional)

In addition, an analysis with different control groups will be carried out. The default control group will be those patients testing PCR-negative to influenza (for IVE studies) or SARS-CoV-2 (for CVE studies). Other control groups will include (where this information is available):

- Patients testing PCR-negative to all respiratory viruses.
- Patients testing PCR-positive to respiratory viruses other than influenza (if IVE) or SARS-CoV-2 (if CVE), for example: rhinovirus, RSV, etc (noting that patients with seasonal coronaviruses are excluded for CVE).
- Patients attending general practitioner (GP) practices for reasons other than a respiratory infection (a traditional case control study) could also be considered, particularly during periods where there may be low circulation of other respiratory viruses (more relevant for CVE).

In the context of a high correlation between influenza and COVID-19 vaccination, control groups can exclude SARS-CoV-2 PCR-positive patients (IVE) or influenza PCR-positive patients (CVE), see section 5.1.7.

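### The primary analysis keeps SARS-CoV-2-positive controls for IVE and influenza-positive controls for CVE, a control set that section 5.1.7 itself calls invalid under strongly correlated vaccination.

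*Protocol*

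**What the plan says.** Section 5.1.7 starts from the requirement that the vaccine under study must not affect the control group. It then warns: "However, there may be a strong correlation between those receiving influenza and COVID-19 vaccine". For that case it gives a direction for each study. For IVE, "inclusion of SARS-CoV-2-positive controls may artificially lower the vaccine coverage among influenza test-negative controls, biasing towards a lower IVE". For CVE, "inclusion of influenza-positive controls may artificially lower the vaccine coverage among SARS-CoV-2 test-negative controls, biasing towards a lower CVE". It concludes: "The test-negative design is no longer valid".

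The next paragraph of 5.1.7 recommends analyses without these controls where the information allows, and adds: "These estimates can be compared to the primary analysis of including SARS-CoV-2-positive/influenza-positive controls". The inclusive set is therefore the primary one. Section 3.5.4 agrees, since its default control is any patient PCR-negative for the study virus. The primary-analysis exclusions in section 3.7.3 do not list influenza-positive controls for CVE or SARS-CoV-2-positive controls for IVE.

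The remedies carry different force in different places:
- Section 5.1.7 commits to them: "Sensitivity analyses will be conducted excluding controls who are positive for SARS-CoV-2 from IVE estimation", with the mirror-image statement for CVE.
- Section 3.5.4, under a heading marked optional, says only that control groups *can* leave these patients out when the correlation is high.
- Section 3.13.2 lists the following among analyses that sites *can* run: "excluding controls testing SARS-CoV-2 positive (IVE) or influenza positive (CVE), or adjusting by COVID-19 (IVE) or influenza (CVE) vaccination".

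Section 3.7.3 does remove seasonal-coronavirus-positive controls from the primary CVE analysis, on the ground that vaccination may affect them.

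**The concern.** The protocol identifies a bias, gives its likely direction and says what it does to the design. It still rests the headline estimate on the control set that carries the bias. No rule says when the exclusion estimate should replace the inclusive one, so under strong correlation the reported IVE or CVE would be the figure that the protocol describes as invalid.

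The treatment of controls is also uneven. One group that vaccination may affect (seasonal coronavirus) is dropped from the primary analysis. Another group, for which the protocol sets out both mechanism and direction, stays in.

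The bias does not shrink as the sample grows. It acts within site and week, so the adjustment for site and onset time that Annex 4 always applies does not remove it. Section 1.2 says that very low early IVE could prompt other interventions, so a downward error can matter for decisions.

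**Working it through.** **Inputs.** The protocol gives no correlation between the two vaccinations, no share of other-virus positives among controls and no VE for the other vaccine. All bias inputs below are assumptions. The 1:1 allocation is from section 3.10.

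**Bias formula.** Let *v* be study-vaccine coverage in the remaining controls, *a* and *b* the uptake of the other vaccine in those with and without the study vaccine, *E* the other vaccine's VE, and *s* the share of controls positive for the other virus. Each vaccine is taken to act only on its own virus.

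- Relative risk of the other virus: r1 = 1 − aE in the vaccinated, r0 = 1 − bE in the unvaccinated.
- Study-vaccine coverage among other-virus positives: c = v·r1 / [v·r1 + (1 − v)·r0].
- Coverage in the mixed control group: m = (1 − s)·v + s·c.
- Apparent VE = 1 − OR × [v/(1 − v)] / [m/(1 − m)].

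Take OR = 0.6 (true VE 40%), v = 0.5, E = 0.5, s = 0.3.

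| Uptake a / b | r1, r0 | c | m | Odds m/(1 − m) | Apparent VE |
|---|---|---|---|---|---|
| equal (a = b) | equal | 0.50 | 0.50 | 1.000 | 40.0% |
| 60% / 40% | 0.7, 0.8 | 0.35/0.75 = 0.467 | 0.35 + 0.14 = 0.49 | 0.961 | 1 − 0.6/0.961 = 37.6% |
| 80% / 20% | 0.6, 0.9 | 0.30/0.75 = 0.40 | 0.35 + 0.12 = 0.47 | 0.887 | 1 − 0.6/0.887 = 32.3% |

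**Range at 80%/20% uptake.**
- IVE, with 10–40% SARS-CoV-2-positive controls and COVID-19 VE 30–50%: 38.7% down to 29.6%.
- CVE, with 20–50% influenza-positive controls and influenza VE 40–50%: 36.3% down to 26.7%.
- CVE with a 5% influenza share and influenza VE 40%, as might apply at the edge of the influenza season: 39.1%.

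**Do the protocol's remedies work?** Excluding the other-virus positives returns coverage to *v*, and VE to 40%. Adjusting for the other vaccine also works in this model. At 80%/20%, half the source population has the other vaccine: 0.40 with both vaccines and 0.10 with the other only, so the odds of study vaccination are 4. Among other-virus positives in that stratum the weights are 0.40 × 0.5 = 0.20 and 0.10 × 0.5 = 0.05, again odds of 4. Mixing the groups within a stratum therefore changes nothing.

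**Precision cost.** First, a Table 4 row to confirm the method (OR 0.5, coverage 50%, precision 0.2). Vaccinated share in cases = 0.25/0.75 = 0.333. Variance term = 3 + 1.5 + 2 + 2 = 8.5. n = 8.5 / [ln(0.7/0.5)/1.96]² = 8.5/0.02947 = 288.4, rounded up to 289, as printed. With 289 cases, losing 10%, 30% or 50% of the 289 controls moves the lower bound from 30.0% to 29.4%, 27.7% or 24.8%.

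For the VE 40% example at 1:1, the vaccinated share in cases is 0.375. Cases contribute 1/0.375 + 1/0.625 = 4.267 and controls 4, total 8.267.

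| Controls lost | Control term | Total | SE ratio |
|---|---|---|---|
| 20% | 5.000 | 9.267 | 1.06 |
| 30% | 5.714 | 9.981 | 1.10 |
| 40% | 6.667 | 10.933 | 1.15 |
| 50% | 8.000 | 12.267 | 1.22 |

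**The case against.** The protocol is open about the bias, gives its direction and offers two remedies. A reader of 3.5.4 and 3.13.2 alone might infer that exclusion is merely optional. The closing commitment in 5.1.7 does not support that: the sensitivity analyses are to be done. What stands is the clash in wording and the choice of headline.

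A reader might also infer that the protocol declares its own primary analysis invalid outright. It does not. The statement applies if vaccination is strongly correlated, and the effect on coverage is worded as a possibility. Models that adjust for age and chronic conditions would absorb part of any correlation arising from shared target groups, and only the correlation that remains would bias the adjusted VE.

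Nor can the cleaner analysis be run everywhere. Annex 1 lists both test results and both vaccination statuses outside its optional rows, but accepts that sites may not collect everything. Sites may study only one virus (section 2). Section 3.6 asks CVE-only sites for influenza testing where feasible and makes no matching request of IVE-only sites. The present default can be applied at every site. A mixed approach would let control definition and covariates differ by site within the one-stage pooled model, which is a real cost.

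Finally, the seasonal-coronavirus exclusion concerns a possible direct effect of the vaccine, whereas here the link runs through correlated uptake. The mechanisms differ, but 5.1.7 places the second under the same requirement that controls be unaffected by vaccination, so the inconsistency remains.

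**Conclusion.** The point holds in conditional form. Where the two vaccinations are correlated, the other virus is present among controls and the other vaccine works, the primary estimate is biased downwards by a route that the protocol describes and can largely close. In the central example a true VE of 40% loses 2.4 points at 60%/40% uptake and 7.7 points at 80%/20%. It loses nothing if uptake is uncorrelated, and little when the other virus is rare among controls. These sizes are illustrative: they are crude odds ratios that rest on assumed coverage, uptake, share and VE.

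It is tempting to add that a changing share of the other virus would create false waning or false between-site heterogeneity. That is plausible, but the protocol gives no figures from which to show it and it was not calculated, so it is not part of this conclusion.

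**What to change.** Amend sections 3.5.4, 3.7.3, 3.13.2 and 5.1.7 together:

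1. Wherever the second test result is available, the primary analysis excludes SARS-CoV-2-positive controls (IVE) and influenza-positive controls (CVE).
2. Where it is not available, adjust for the other vaccination, and report those sites separately or in a sensitivity analysis of the pooled model.
3. Keep the all-test-negative control group as a sensitivity analysis that *will* be run, with the same verb in every section.

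The cost is protocol wording, fewer controls with the loss of precision shown in the working, and some difference between sites in how the bias is handled. The last should be stated when pooled results are reported.
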